Title of the study: Effect of stimulation of the dorsolateral prefrontal cortex on language production (study A) and motor control (study B)

**Principal investigator:
[name]**

Study A) Effect of stimulation of the dorsolateral prefrontal cortex on language production in healthy bilinguals – Second addendum

Background:

Language relies on two main neurocognitive components; a dedicated language network depending on perisylvian structures, and a domain-general control-executive and working memory system relying on prefrontal, particularly left cingulum and dorso-lateral prefrontal cortex (DLPFC) networks. The executive system is known to participate in language control in bilinguals, but also plays a role in many intra-languages processing, for mother language (L1) and even more in second language production (L2). For instance, the lexical access in L2 requires more left frontal activation than in L1. The integrity of language control has been associated with a parallel recovery of L1 and L2 in aphasia in bilinguals (Green et al., 2010 [1]) and increased connectedness of the control and language networks has been associated to L2 recovery after therapy (Abutalebi et al., 2009 [2]).

Repetitive transcranial magnetic stimulation (rTMS) is increasingly being used as promising therapeutic tool for psychiatric and neurological diseases as well as a valuable tool for neuroscientists investigating underlying mechanisms of cognitive functions (Machii et al., 2005 [3], Lefaucheur et al., 2014 [4]). Several studies investigating healthy or clinical populations have shown that (r)TMS applied to the left dorsolateral prefrontal cortex (DLPFC) has an effect on language-related processes such as verbal working memory (Osaka et al., 2007 [5]), sentence comprehension (Cotelli et al., 2011 [6]) and language switching (Holtzheimer et al., 2005 [7], Nardone et al., 2011 [8]).

Clinical observations and neuroimaging studies seem to confirm the role of executive functions and frontal structures in language processing in monolingual and bilingual subjects (e.g. Fabbro et al., 2000 [9], Abutalebi & Green 2007 [10]). However, there are only few studies investigating the effect of rTMS applied to the prefrontal cortex on language processes such as verbal working memory and switching, for which executive functions seem to be crucial.

Aim:

The aim of the present project is to demonstrate the impact of the modulation of executive functions, particularly subserved by DLPFC, on language production in healthy bilingual. We propose that such impact will be particularly present in non-native languages (L2).

The project will tackle the question of the role of prefrontal system and executive functioning (namely updating/working memory system, subserved by the left DLPFC) in language performance in the L1 and in L2. The core question will be whether stimulation of DLPFC will influence lexical access and language production.

The experimental task will test the impact of prefrontal stimulation by rTMS (excitatory, inhibitory, sham) applied to the DLPFC of healthy adult bilingual subjects during two tasks relying on lexical strategies: a picture naming task in L1 and L2 and a word translation task. The EEG correlates of the two tasks performed in the first and second language following rTMS will be analyzed. The EEG study will allow us to investigate precisely the spatiotemporal brain dynamics underlying the behavioral modifications induced by the modulation of left frontal areas.

The hypothesis is that:

1. Excitatory rTMS applied to the left DLPFC will increase performance and/or decrease response time in naming, particularly in L2 naming and in the translation task versus sham and inhibitory rTMS.
2. Excitatory rTMS is expected to modify the cortical activity related to the language tasks. During naming, EEG analyses will show a main effect of stimulation and an interaction between the factors Language (L1 or L2) and Stimulation (excitatory rTMS versus sham and inhibitory rTMS versus sham) at the topographic level, showing an effect of prefrontal areas larger in L2 than L1. The latency of the ERP modulation by rTMS in L2 will allow us to target the dynamics and the language planning processes) underlying improved naming performance.

Methods:

The experimental task will include 80 healthy L1-L2 unbalanced control subjects. We will analyze the influence of the DLPFC activation and inhibition on naming and complex language production task (i.e. translation ability) using rTMS as well as their EEG correlates in L1 and in their best second language (L2). The prediction is that left prefrontal stimulation will increase language performances particularly in L2. EEG analyses will unravel the spatio-temporal dynamics of executive processes involved in the two tasks.

EEG

EEG is a direct non-invasive technique for recording of the electrical activity produced by neurons over the scalp with a high temporal resolution. EEG recordings recording is obtained by placing electrodes on the scalp, with a conductive gel filling the distance between electrode and scalp. The electrodes are then connected to an amplifier to amplify and convert the signals as digital voltage values. The event-related potentials will be processed/analyzed offline. A 64 channel Biosemi ActiveTwo system will be used for the recordings.

rTMS

TMS is a painless and non-invasive method of brain stimulation which has gained considerable interest worldwide for clinical as well as neuro-scientific use. Applying TMS leads to neuronal depolarization which has an excitatory or inhibitory effect on the cortex (Rothwell, 1997 [11]). By using changes in magnetic fields to create electric currents, TMS allows modulating cortical excitability and as such stimulating focal brain areas (Walsh & Pascual-Leone, 2003 [12]). Depending on the frequency, intensity and duration of the stimulation, repetitive TMS (rTMS) can lead to temporary increases or decreases in excitability of the affected cortex, which have been shown to last for several minutes beyond the duration of the stimulation itself (Lefaucheur et al., 2014 [4]).

Sham rTMS (or placebo rTMS) refers to a control condition in which no physiological effect on the targeted cortical region should occur. For sham rTMS it is important, that the subject is not aware that he/she is receiving a placebo-stimulation. As such, placebo rTMS needs to fulfill a number of criteria (Loo et al., 2000 [13]) so that it has no effect on the targeted cortical region while at the same time appearing as similar as possible to real rTMS.

By comparing the results in subjects receiving sham rTMS with the results of subjects receiving excitatory or inhibitory rTMS, researchers can determine how much of an effect is caused by rTMS, rather than by a potential placebo effect.

Language proficiency assessment

The participants should have an intermediate level of English knowledge (based on a self-

evaluation questionnaire and DIALANG)

To assess language immersion, participants will be asked for the age of acquisition, how long they lived in a region where predominantly German and English language was spoken, the language spoken with family members, when they were child, in their current daily life, and if the language was acquired in or out of school. With regards to the self-evaluation part, participants will indicate in an analogue scale from 1 to 100% how they estimate their reading, speaking, comprehension and writing skills. As a third level of assessment, a sub-test from the computer-based DIALANG language diagnosis system (Zhang and Thompson, 2004 [14]) will be used to evaluate reading performance (see Buetler et al 2014 for a similar procedure [15]).

Procedure

Participants will be randomized to take part in either an inhibitory or excitatory rTMS session. In all sessions, the same evaluations/tasks will be used. Each session starts with sham rTMS-controlled baseline tasks.

At the beginning of the session, the individual motor threshold for the subject's relaxed small hand muscles will be determined by stimulating the right motor cortex with single pulses (e.g. Nyffeler et al., 2008 [16]). This will last about 5-10 minutes. For the rTMS session, we will be using a "theta-burst" rTMS protocol (Nyffeler et al., 2008 [16]; Huang et al., 2005 [17]), in which one of the co-applicants has extensive experience. This stimulation takes 30 seconds to 5 minutes and the resulting effects have been shown to last about 30 minutes. Each rTMS session will be conducted following suggested international rTMS guidelines (Wassermann et al., 1998 [18]).

After applying rTMS, two language tasks will be performed by the participants while an EEG will be recorded. The two language contexts (German and English) will be presented within each of the two sessions in a randomized order. EEG electrodes will be applied before the stimulation. Participants will be seated in an electrically shielded and sound attenuated booth in front of a LCD screen. Stimulus delivery and response recording are controlled using E-Prime 2.0 (Psychology Tools, Inc., Pittsburgh, PA). The stimuli will be presented in the center of the screen. Both behavioral and EEG data will be recorded.

Stimuli and tasks

This study will be conducted in parallel to the previously accepted study A. For this second addendum, there will be no translation task and a different non-verbal task.

Verbal and nonverbal switching task during EEG recording

Right after applying rTMS (inhibitory/excitatory/sham), participants will perform a language switching task during the EEG recording. The switching task will be based on a corpus of 520 pictures, the corresponding words being matched in English and German on pertinent psycholinguistic factors (Bates et al 2003 [19]). The stimuli consist of black and white line drawings (of 8.5 x 8.5cm each) representing manufactured or living objects. Right before the picture appears on the screen, a cue will be given to the participants in order to indicate the language in which they have to name the object. The subject will then have 3500 - 4500 ms to name the object.

Moreover, participants will also perform a non-verbal switching task during the EEG recording. In this task, participants have to switch frequently between high/low and odd/even classifications of a digit, based on the method of Monsell, Sumner and Waters (2003) Before each digit appears, a cue will be given to indicate to which classification criteria participants have to respond.

Translation task to L1 and L2 during EEG recording

Moreover, participants will perform a task consisting of translating 100 words (5 letters length) from L1 to their second language (L2) or vice versa (8 minutes). Both senses of translation will be mixed randomly to increase working memory load. Translation corpus consists of 50 words in each language, matched across L1 and L2 on frequency, length in syllables and phonemes. Words will be presented on the screen and the subject will be asked to translate each word in the other language. The words will be presented 1500 ms on the screen after a fixation cross of 300ms. The subject will have a maximum 2500ms to do the translation.

Verbal and non-verbal fluency tasks, without EEG recording

With the specific stimulation parameters used in our protocol, 30 minutes after applying rTMS (inhibitory/excitatory), it can be assumed that the after-effect of the stimulation will have disappeared. Participants will then perform a verbal fluency task (the subject will be asked to name as many words as he/she can which starts with a certain letter during 1 minute). Furthermore, a non-verbal fluency task (5 points test, i.e. a sheet of paper with 40 squares of fixed symmetrically arranged points (5 points) will be presented to the participant. The participant will be asked to produce as many different figures as possible with connecting the dots with at least one line connecting two dots during 2 minutes). Finally, participants will perform a 1-minute verbal fluency task in L2.

Behavioral and EEG analyses

Behavioral analysis

A first behavioral analysis will compare naming and translation performances, as well as speech onset latencies in both languages.

For statistical analyses we will compute two 2 way-ANOVAs for repeated measures with the within-subject factors *Language* (L1 vs L2) and *Stimulation* (inhibitory vs sham or excitatory vs sham). Moreover, we will compute two mixed-model ANOVAs with *Language* (L1 vs L2) as within-subject factor and *Hemisphere* (left vs. right) or *Stimulation* (inhibitory vs excitatory) as between-subject factors.

Event Related Potentials analyses

The analyses will be conducted with the same principles as in our prior works with reading and naming tasks. ERPs will be analyzed using a step-wise procedure that permits the time-wise, multifactorial statistical assessment of (1) the dynamic changes of scalp-recorded electric field configuration and their temporal segmentation into quasi-stable functional micro-states indexing modulations of the configuration of intracranial generators, (2) global electric field power indexing modulation of response strength of the intracranial generators, (3) intracranial distributed linear electrical source estimations (e.g. Brunet et al., 2011 [21]; Murray et al., 2008 [22]). These analyses will be conducted for each time frame of the whole ERP time-period; however, specific time windows are planned to be sensitive to our factors according to meta-analyses [19] and our previous results: lexical selection is thought to occur between 170 and 270 ms after picture presentation, so there will be a first time window until 200 ms, a second time window between 200 and 300 ms, and a later time window (300-450 ms) corresponding to lexical-phonological encoding in previous studies. The main effect will be L1 and L2 patterns in term of amplitude, duration and sequences. Then, a second main effect will be the left inhibitory/excitatory/sham effect in an early time window before the vocalization will start. We will expect an interaction between language and stimulation, due to the fact that left DLPFC excitatory rTMS will modulate L2 more than L1.

References

1. Green, D.W., et al., Language control and parallel recovery of language in individuals with aphasia. *Aphasiology*, 2010. 24(2): p. 188-209.
2. Abutalebi, J., et al., Bilingual aphasia and language control: a follow-up fMRI and intrinsic connectivity study. *Brain Lang*, 2009. 109(2-3): p. 141-56.
3. Machii K. et al. 2006. Safety of rTMS to non-motor cortical areas in healthy participants and patients. *Clinical Neurophysiology*, 117, 455-471.
4. Lefaucheur JP et al., 2014. Evidence-based guidelines on the therapeutic use of repetitive transcranial magnetic stimulation (rTMS). *Clinical Neurophysiology*, 125, 2150-2206.
5. Osaka N et al., 2007 Transcranial magnetic stimulation (TMS) applied to the left dorsolateral prefrontal cortex disrupts verbal working memory performance in humans. *Neuroscience Letters*, 418, 232-235.

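### Study A always runs sham before active rTMS, so the within-arm active-versus-sham main effect cannot be separated from run order

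*Combined protocol and SAP*

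**What the plan says.** Under Procedure, Study A randomises participants to an inhibitory or an excitatory rTMS session, and language order is randomised within sessions. The order of sham and active stimulation is fixed: "Each session starts with sham rTMS-controlled baseline tasks". The task section confirms that the same task follows either kind of stimulation: "Right after applying rTMS (inhibitory/excitatory/sham), participants will perform a language switching task".

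Under Behavioral analysis, "we will compute two 2 way-ANOVAs for repeated measures with the within-subject factors" Language and Stimulation, the latter with levels "inhibitory vs sham or excitatory vs sham". Mixed ANOVAs are also planned, one of them with Stimulation ("inhibitory vs excitatory) as between-subject factors").

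Hypothesis 1 predicts that excitatory rTMS is better than both sham and inhibitory rTMS. Hypothesis 2 predicts a stimulation main effect on the EEG and a Language by Stimulation interaction, with each active type set against sham. The rTMS section says in general terms that by comparing sham with active stimulation "researchers can determine how much of an effect is caused by rTMS".

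Two places bear on why sham comes first. Procedure says of theta-burst stimulation that "the resulting effects have been shown to last about 30 minutes". The fluency-task section says that 30 minutes after rTMS "it can be assumed that the after-effect of the stimulation will have disappeared". Counterbalancing of session order is stated for Study B. Nothing similar is stated for sham and active in Study A.

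**The concern.** If sham is always the first run and active always the second, the sham-to-active change contains everything else that differs between a first and a second run: familiarity with the task, repeated items, warm-up and fatigue. The within-arm ANOVA has no means of separating these from stimulation.

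The parts of hypotheses 1 and 2 that compare with sham are at stake. Faster or more accurate naming on the second run would look like the predicted excitatory benefit. The same gain in the inhibitory arm could hide a real loss. Any within-arm sham contrast on the ERP measures has the same weakness; the ERP section lists a stimulation effect that includes sham but does not specify its test.

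**Working it through.** **1. Can the effect be estimated?** The plan gives no figure to reproduce here, so the first check is on the design itself.

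- *One arm, fixed order.* Terms: intercept, Language, Stimulation, run order. Stimulation and run order are the same column (0 for the sham run, 1 for the active run). The design matrix has rank 3 of 4, so the main effect is fully aliased.
- *Both arms, common order effect.* Terms: intercept, arm, run order, excitatory effect, inhibitory effect. Rank is 4 of 5. Neither effect against sham is estimable; their difference is.
- *Sham/active order counterbalanced.* Rank is 4 of 4, so the effects separate if there is no carry-over.

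This result needs no numerical assumption.

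**2. How large could the consequence be?** From the documents: 80 participants and two randomised stimulation types. Assumed, because the documents do not give them: a 1:1 split (n = 40 per arm), two-sided α = 0.05, no true rTMS effect, a second-run gain g in SD units, and a sham-active correlation r of the language-averaged score.

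In a two-level within-subject design, the Stimulation main effect is a paired t test on the language-averaged change. The change has SD √(2(1−r)), so the standardised shift is d = g/√(2(1−r)). The rejection rate comes from a noncentral t with 39 degrees of freedom and noncentrality d√40.

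| g | r = 0.5 | r = 0.7 | r = 0.8 |
|---|---|---|---|
| 0.2: d | 0.200 | 0.258 | 0.316 |
| 0.2: rejection | 23.5% | 35.7% | 49.6% |
| 0.1: rejection | 9.5% | 12.5% | 16.4% |

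A simulation of 20,000 trials per scenario gave 23.5%, 35.8% and 49.8% for the 0.2 SD row.

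Variations at g = 0.2:

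- *At least one arm significant,* 1 − (1−p)²: 41.4%, 58.6%, 74.6%. With no order effect it is 1 − 0.95² = 9.75%.
- *SD and r taken for single-language scores under compound symmetry.* The change variance becomes 1 − r, and the rates are 41.5%, 61.5%, 78.8%.
- *20 per arm:* 13.6%, 19.5%, 26.9%.

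**3. Masking.** Suppose a true inhibitory loss of 0.4 SD and a practice gain of 0.2 SD. The net loss is 0.4 − 0.2 = 0.2 SD. Power falls from 69.4%, 89.0% and 97.4% to 23.5%, 35.7% and 49.6%.

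**4. Language by Stimulation interaction within an arm.** If both languages gain equally, the order effect cancels and the rate stays at 5%. If L2 gains more than L1 by 0.2 SD of the L2-minus-L1 difference, and the sham and active differences correlate 0, 0.3 or 0.6, then d = 0.2/√(2(1−ρ)) = 0.141, 0.169, 0.224. The rejection rates are 14.1%, 18.1% and 28.1%.

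**5. The randomised comparison.** Both arms have the active run in the same position, so a common order effect cancels. In simulation, an ANCOVA of the active-phase score on arm with the sham-phase score as covariate rejected in 4.7% to 5.3% of trials in every scenario.

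The detectable arm difference at 80% power with 40 per arm is 0.634 SD without the covariate. With it, multiply by √(1−r²): 0.549, 0.453 and 0.381 SD for r = 0.5, 0.7 and 0.8. For the L2-minus-L1 difference at ρ = 0, 0.3 and 0.6 it is 0.634, 0.605 and 0.508 SD.

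**The case against.** The strongest reply is that only one of several planned tests is affected. The randomised excitatory-versus-inhibitory ANOVA is already in the plan, and the main scientific interest is the L2-specific interaction. Hypothesis 1 requires excitatory to beat both sham and inhibitory; practice alone can produce the first result but not, beyond chance, the second. This is correct and limits the damage. It does not rescue the comparison with sham, which both hypotheses name and for which two ANOVAs are planned. Nor is the interaction fully safe: participants are unbalanced bilinguals, so equal practice gains in L1 and L2 cannot be taken for granted.

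Sham first also has a likely reason, though the documents do not state it. With an after-effect of about 30 minutes, sham after active in one session would risk carry-over. That supports keeping the sequence, but not the causal reading of the change.

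The figures rest on assumptions, and some illustrations are weaker than others. The either-arm rate counts improvement after inhibitory rTMS, which hypothesis 1 does not predict; the single-arm rate is the more relevant one. Hypothesis 1 states no inhibitory loss against sham, although the analysis tests that contrast. The 20-per-arm case applies only if the Hemisphere factor, named for the mixed ANOVAs, also splits these analyses. The 5% rate for the randomised test assumes an order effect common to both arms.

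This is an addendum to a study A protocol that is not included. Separate picture lists may be planned, since the corpus has 520 pictures; general practice and fatigue would remain. Hypothesis 1 also mentions translation, which this addendum drops, but naming is still affected. The rTMS section's sentence on sham is general background rather than a statement about run order.

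**Conclusion.** The concern holds. As planned, the within-arm active-versus-sham main effect is completely confounded with run order, and no other section repairs this. That conclusion follows from the design and is independent of the numerical assumptions. The actual bias is unknown. A modest second-run gain of 0.2 SD would raise a single arm's false-positive rate from 5% to roughly 23% to 50% with 40 per arm and correlations of 0.5 to 0.8; a gain of 0.1 SD would raise it to roughly 9% to 16%.

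The finding is limited to contrasts with sham. The interaction is exposed only if order effects differ between languages, and the part of hypothesis 1 that compares excitatory with inhibitory rests on randomisation. Because the hypotheses explicitly claim effects against sham, the plan should be corrected.

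**What to change.** Keep the sham-first sequence and change the inference:

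- Make the planned randomised excitatory-versus-inhibitory comparison, and its interaction with Language, the confirmatory test for behaviour and ERP.
- Use the active-phase score as outcome and the sham-phase score as covariate. For the interaction, use the L2-minus-L1 difference with the sham-phase difference as covariate. The plan does not define the score for this ANOVA; leaving out the sham score would lose precision but would not be an error.
- Report within-arm sham-to-active changes as descriptive, and state that they do not isolate an rTMS effect.
- Reword the parts of hypotheses 1 and 2 that compare with sham.
- State, or cite from the parent study A protocol, whether pictures repeat between the sham and active runs.
- Separately, reconcile the Procedure section's reference to two sessions with its randomisation to one session type. Sham comes first on either reading.

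No new data are needed. The cost is in the claims: the conclusion becomes excitatory versus inhibitory and cannot show which arm differs from sham. A causal claim against sham would need a design change that also deals with the roughly 30-minute after-effect, such as order-balanced separate sessions or a sham-then-sham group. Simple counterbalancing within one session would risk carry-over.

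### Study A's naming task is a cued language-switching task, but no model separates switch from repeat trials, so an rTMS effect on naming could not be attributed to lexical access.

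*Combined protocol and SAP*

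**What the plan says.** All places are in Study A of the combined protocol and SAP.

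- **Aim.** "The core question will be whether stimulation of DLPFC will influence lexical access and language production". The tasks are introduced as "a picture naming task in L1 and L2 and a word translation task", without mention of switching. Hypothesis 1 predicts better or faster naming under excitatory rTMS, above all in L2.
- **Verbal and nonverbal switching task during EEG recording.** Here "participants will perform a language switching task during the EEG recording". "The switching task will be based on a corpus of 520 pictures", and just before each picture "a cue will be given to the participants in order to indicate the language in which they have to name the object". The number of trials, the share of switch trials and the rule for the cue sequence are not given.
- **Procedure.** "The two language contexts (German and English) will be presented within each of the two sessions in a randomized order".
- **Behavioral analysis.** Naming performance and speech onset latency are compared by language. The repeated-measures ANOVAs use Language and Stimulation. The mixed ANOVAs use Language within subjects, with Hemisphere or Stimulation between subjects.
- **Event Related Potentials analyses.** The expected interaction is Language × Stimulation, and the time windows are interpreted as lexical selection and lexical-phonological encoding.
- **Background.** Stimulation of the left DLPFC "has an effect on language-related processes such as verbal working memory"; the same sentence goes on to list language switching.

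No section defines repeat and switch trials, a switch cost or a trial-type factor.

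**The concern.** When the naming language is cued picture by picture, every trial after the first either repeats the previous language or switches. Switching may add a cost to latency and accuracy that comes from language control rather than from retrieving the word. A model with only Language and Stimulation averages over both kinds of trial.

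The comparison with sham removes the switch cost common to active and sham stimulation. It does not remove a change in that cost caused by rTMS, and the Background itself names switching among the processes that stimulation of this site affects.

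No other verbal measure fills the gap. The section on stimuli and tasks says that this addendum drops translation, and verbal fluency is tested once the after-effect is assumed to have gone. A Stimulation effect on pooled naming could therefore be reported as an effect on lexical access when it arose in language control, or a lexical effect could be masked. The effect on verbal switching itself would go unestimated.

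**Working it through.** The plan gives no figure to reproduce: 80 participants are stated for Study A, without alpha, power, effect size or SD. The check is therefore to work out what the stated model estimates.

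**Algebra.** Let p be the share of switch trials, equal in active and sham. Let b be the rTMS effect (active minus sham) on repeat-trial latency, and d the rTMS-induced change in switch cost. Mean pooled latency in a condition is repeat-trial latency + p × switch cost. Hence:

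- pooled Stimulation effect = b + p × d
- pooled Language × Stimulation (L2 minus L1) = (b2 − b1) + p × (d2 − d1)

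If d1 = d2 in milliseconds, the second contamination term is zero, however unequal the baseline costs. If p differed between active and sham, a part of the baseline switch cost would also enter.

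**Illustration 1: a proportional change (all values assumed).** Suppose rTMS changes both costs by a fraction r, with p = 0.5.

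- Mean cost 75 ms, r = 0.3: Stimulation shift = 0.5 × 0.3 × 75 = 11.25 ms.
- Cost difference between languages 50 ms, r = 0.3: interaction shift = 0.5 × 0.3 × 50 = 7.5 ms.
- Range: 0.5 × 0.2 × 20 = 2 ms to 0.5 × 0.5 × 50 = 12.5 ms. The equal-shift case adds 0 ms.

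The sign depends on direction. If rTMS reduces the cost and switching into L1 costs more, the L1 gain is larger, which works against hypothesis 1. It favours the hypothesis if switching into L2 costs more. Both signs reverse if rTMS raises the cost.

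**Illustration 2: how often the pooled test is significant when b = 0.** Assume 40 participants per stimulation type (an equal split of 80), a paired contrast, two-sided 0.05, a normal approximation and d = 20 ms. For p = 0.5 and SD 50 ms, the shift is 0.5 × 20 = 10 ms and the SE is 50/√40 = 7.91 ms. The ratio is 1.265, and Φ(1.265 − 1.96) + Φ(−1.265 − 1.96) = 0.244.

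| p | shift (ms) | SD 30 ms | SD 50 ms | SD 80 ms |
|---|---|---|---|---|
| 0.25 | 5 | 18.4% | 9.7% | 6.8% |
| 0.50 | 10 | 55.9% | 24.4% | 12.4% |
| 0.75 | 15 | 88.5% | 47.5% | 22.0% |

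These are not false positives for pooled naming latency, which does change. They are the chance of a significant result that says nothing about repeat-trial naming. A repeat-trial contrast has no p × d term and rejects at 5% when b = 0.

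**Feasibility of the split.** If 520 trials are run per stimulation condition (assumed), each language has 260, and p = 0.5 leaves 260 × 0.5 = 130 repeat trials per Language × Stimulation cell. If the 520 pictures are shared between active and sham, 65 remain. At p = 0.75 the figures are 65 and 32.5.

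**The case against.** - **The study is also about executive control.** The aim is to show how modulating executive functions affects language production, and hypothesis 1 is worded in terms of naming performance. An effect that runs through switching is partly what is sought. This stands. A reader might infer that the planned test cannot answer the study's question at all. The documents do not support that: pooled naming can test hypothesis 1 as written. What fails is attribution to lexical access or lexical selection.
- **The languages may be blocked.** The Procedure's wording on language contexts can be read so, and the concern would then largely fall away. But the task section is the more specific text and describes a cued switching task. The two need reconciling either way.
- **Pooling is inferred.** The behavioural plan is called a first analysis and never says that trials are pooled. That is fair, but every model it states would pool them.
- **The evidence on switching is indirect.** Judging by their titles, one cited source concerns rTMS inducing switching in bilingual patients and the other is a case report of pathological switching. Neither title refers to cued switch cost in healthy bilinguals. A change in switch cost is therefore plausible here, not established.
- **The task's purpose.** A reader might also infer that the addendum introduced the verbal task to demonstrate a switching effect. The changes it lists are only the dropped translation task and a different non-verbal task.

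**Conclusion.** The concern holds as a limit on interpretation. Under the plan as written, any rTMS-induced change in switch cost enters the pooled Stimulation effect with weight p, and the sham comparison does not remove it. This follows from the cued task and the stated factors, provided that languages are mixed within a run.

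It would go too far to infer that any such change also creates a spurious Language × Stimulation interaction. That requires the change to differ between L1 and L2, and the documents give no basis for its size or sign.

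The size is unknown. The 2 to 12.5 ms interaction shift and the 24.4% rejection rate (12.4% to 55.9% for SDs of 80 to 30 ms at p = 0.5) illustrate assumed switch shares, costs and SDs. Nor is the ambiguity necessarily built into the data: if the cue order is kept, trials can be classified and most of the problem removed in the analysis.

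**What to change.** 1. Reconcile the Procedure with the task section: state whether German and English are blocked or cued picture by picture within a run.
2. If they are mixed, state the switch share, keep it balanced across Language and Stimulation, and record the cue sequence. The plan says that software controls stimulus delivery and response recording, but not that cue order is stored or balanced.
3. Add Trial type (repeat vs switch) as a within-subject factor to the behavioural and ERP models for the verbal task.
4. Report Language × Stimulation on repeat trials beside the pooled result, and report Trial type × Stimulation and Trial type × Language × Stimulation as the switching effect.
5. Confine claims about lexical access to what the repeat-trial results support.

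The cost is mainly wording if the sequence is already balanced and stored; otherwise the task programme must change too. Cells become smaller and repeat-trial estimates less precise. Repeat trials in a mixed-language task still carry a mixing cost, so they reduce the language-control component without removing it. Only single-language blocks would remove that as well.
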